#### 13.1 CRITERIA FOR REMOVAL FROM STUDY

All patients may continue therapy unless disease progression, death, or dose limiting toxicity is documented. The cause of death should be recorded.

The following events may be considered sufficient reason for discontinuing treatment with the study medication

- Serious toxicity due to the study drug graded according to the NCI Common Terminology Criteria for Adverse Events v3.0 [22]
- Conditions requiring therapeutic intervention not permitted by the protocol
- Unacceptable toxicity in the opinion of the patient or investigator even if not specifically defined elsewhere
- Personal preference by the patient for any reason
- Subject non-compliance with the defined treatment plan
- Medical or psychiatric illness or social environment which in the investigator's judgment renders the patient incapable of further therapy.
- Any other situation where, in the opinion of the investigator, continued participation in the study would not be in the best interest of the patient
- Treatment delay due to toxicity greater than 14 days
- Pregnancy
- Disease progression

All reasons for discontinuation of treatment must be documented in the flow sheets.

### IRB#: 06-044 A(11)

#### .0 **BIOSTATISTICS**

The historical values for comparison are from a database of 225 GBM patients enrolled in 8 previous phase II studies (in which none of the treatments were considered particularly effective.[24] In this database, the 6 month PFS was 15% for GBM. The 6 month PFS for patients treated with BCNU for recurrence/progression was 17.5%.[3] Therefore, we would expect 6 month PFS to be less than 20%.

We will utilize a Simon two-stage design in which the primary endpoint is the progression rate at 6 months. All patients will be followed for 6 months and progression or death due to disease will be considered an event. Assuming a 6 month progression free survival rate of 20% is considered promising, a 6 month progression free survival rate of 5% is considered not promising, and the probabilities of a type I error (falsely accepting a non-promising therapy) and type II error (falsely rejecting a promising therapy) are set at 0.10 and 0.10, respectively. In the first stage of this design, 12 patients with GBM will be accrued. If at least 1 patient with GBM does not progress at the 6 month time among these 12 patients, then an additional 25 patients with GBM (for a total of 37) will be accrued to the second stage, otherwise the trial will be terminated. Note that enrollment of patients with both GBM and non-GBM malignant gliomas will continue while the first 12 patients with GBM are followed for PFS. However, if 0 of these first 12 reach 6mPFS, then enrollment will terminate; in that event, any patients still on trial with any histology may continue until progression or death at the discretion of the treating physician. At the end of the trial, if 3 or less patients with GBM are progression free at 6 months, the study will be declared negative. This design yields at least a 0.90 probability of a positive result if the true response rate is at least 20% and yields a 0.90 probability of a negative result if the true response rate is 5%.

Up to 20 patients with anaplastic glioma and evaluable disease at study entry (i.e., did not undergo gross total resection as the most recent therapy prior to registration) will be accrued. Endpoints such as response, one-year survival probability, overall survival and progression-free survival will be computed in order to gain preliminary data for these other malignant glioma subtypes. However, the historical controls for patients with anaplastic glioma are less well defined than for GBM; therefore, only patients with GBM will be included in analyses of efficacy and the two-stage design will be applied only to the GBM cohort.

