#### 12.0 CRITERIA FOR THERAPEUTIC RESPONSE/OUTCOME ASSESSMENT

The primary efficacy endpoint will be progression free survival (PFS) at six months from registration. For this and for all other time to event analyses, if a patient is NOT registered on the pre-operative portion of the study (surgical arm), the start date for calculation of time to event will be the date of first study drug administration. For this and for all other time to event analysis, if a patient IS enrolled on the pre-operative portion of the study (surgical arm), the start date for calculation of time to event analysis, if a patient IS enrolled on the pre-operative portion of the study (surgical arm), the start date for calculation of time to event will be the date of the first post-operative study drug administration.

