## IRB#: 06-044 A(11)

Objective status should be measured and recorded although this is not the primary endpoint. The following definitions will be used based on standard criteria for malignant glioma trials [23]:

Measurable Disease: Bidimensionally measurable lesions with clearly defined margins by CT or MRI scan.

Evaluable Disease: Unidimensionally measurable lesions, masses with margins not clearly defined.

Non-Evaluable Disease: Not Applicable for response evaluation

Objective Status, To Be Recorded at Each Evaluation: If there are too many measurable lesions to measure at each evaluation, choose the largest two to be followed before a patient is entered on study. The remaining lesions will be considered evaluable for the purpose of objective status determination. Unless progression is observed, objective status can only be determined when ALL measurable and evaluable sites and lesions are assessed.

Complete Response (CR): Complete disappearance of all measurable and evaluable disease. No new lesions. No evidence of non-evaluable disease. All measurable, evaluable and non-evaluable lesions and sites must be assessed using the same techniques as baseline. Patients must be on no steroids.

Partial Response (PR): Greater than or equal to 50% decrease under baseline in the sum of products of perpendicular diameters of all measurable lesions. No progression of evaluable disease. No new lesions. All measurable and evaluable lesions and sites must be assessed using the same techniques as baseline. The steroid dose at the time of the scan evaluation should be no greater than the maximum dose used in the first 8 weeks from initiation of therapy.

Partial Response, Non-Measurable (PRNM): Not applicable.

Stable/No Response: Does not qualify for CR, PR, or progression. All measurable and evaluable sites must be assessed using the same techniques as baseline. The steroid dose at the time of the scan evaluation should be no greater than the maximum dose used in the first 8 weeks from initiation of therapy.

Progression: 25% increase in the sum of products of all measurable lesions over smallest sum observed (over baseline if no decrease) using the same techniques as baseline, OR clear worsening of any evaluable disease, OR appearance of any new lesion/site, OR clear clinical worsening or failure to return for evaluation due to death or deteriorating condition (unless clearly unrelated to this cancer).

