## IRB#: 06-044 A(11)

Unknown: Progression has not been documented and one or more measurable or evaluable sites have not been assessed.

Best Response: This will be calculated from the sequence of objective statuses.

For patients with all disease sites assessed every evaluation period, the best response will be defined as the best objective status. If the response does not persist at the next regular scheduled MRI, the response will still be recorded based on the prior scan, but will be designated as a non-sustained response. If the response is sustained, e. g. still present on the subsequent MRI, it will be recorded as a sustained response, lasting until the time of tumor progression. Best response is unknown if the patient does not qualify for a best response or increasing disease and if all objective status determinations before progression are unknown.

Criteria permitting uni-dimensional response measurement have recently been adopted and published by an international consensus committee, Response Evaluation Criteria In Solid Tumors Group (RECIST). In order to ensure comparability of data from this trial with data from earlier trials, this trial will retain the traditional evaluation definition above as primary. However, RECIST criteria that can be collected, will be used for secondary evaluation.

Neurological Exam: Although not used for determining response, it is useful to evaluate improvement in the neurologic exam, (as compared to the baseline assessment), that should coincide with objective measurement of tumor size.

- +2 Definitely better
- +1 Possibly better
- 0 Unchanged
- -1 Possibly worse
- -2 Definitely worse

Performance Status: Patients will be graded according to Karnofsky Performance Status (see Appendix 20.1).

Time to Treatment Failure: From the treatment start date to the date of first observation of progressive disease, non-reversible neurologic progression or permanently increased steroid requirement (applies to stable disease only), death due to any cause, or early discontinuation of treatment. If a patient is NOT registered on the pre-operative portion of the study (surgical arm), the start date for calculation of time to event will be the date of first study drug administration. If a patient IS enrolled on the pre-operative portion of the study (surgical arm), the start date for calculation of time to event will be the date of the

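### The primary six-month PFS rule counts only disease deaths as events, so a clearly unrelated death before progression is not an event, and the plan does not say how that patient enters the two-stage counts

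*Combined protocol and SAP*

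**What the plan says.** Section 12 states: "The primary efficacy endpoint will be progression free survival (PFS) at six months from registration". The Biostatistics section (14.0 in the table of contents) instead says that "the primary endpoint is the progression rate at 6 months", and then defines the event: "progression or death due to disease will be considered an event". The 5% and 20% hypotheses, and the historical 15% and 17.5%, are all given as six-month PFS rates.

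The progression definition in Section 12 includes "failure to return for evaluation due to death or deteriorating condition (unless clearly unrelated to this cancer", with the bracket closing there. Deaths of uncertain cause, and absence because of deterioration, therefore count as progression. Only deaths clearly unrelated to the tumour are left out.

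The Biostatistics section describes success in three ways:

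- First-stage rule: "If at least 1 patient with GBM does not progress at the 6 month time among these 12 patients"
- The same rule restated: "if 0 of these first 12 reach 6mPFS, then enrollment will terminate"
- Final rule: "if 3 or less patients with GBM are progression free at 6 months, the study will be declared negative"

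No section says whether a patient who dies of an unrelated cause before progression is a success, a failure, censored or excluded.

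**The concern.** Progression-free survival normally requires the patient to be alive as well as free of progression. Here the definition and the name disagree. Section 12's progression definition and the Biostatistics event rule agree with each other on the narrower version, so this is not a single loose phrase.

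The decision turns on very few patients. One success among the first 12 opens stage 2. At the end, 3 of 37 (8.1%) is negative and 4 of 37 (10.8%) is positive. The trial is single-arm. If an unrelated or drug-related death occurred before progression, its handling would have to be settled after the fact, with the patient's outcome known. A rate reported as PFS but counting only disease deaths would also not be the quantity its name states, nor clearly comparable with the historical PFS rates.

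**Working it through.** **Inputs from the Biostatistics section.** Stage 1 has 12 patients with GBM; stop if 0 succeed. The total is 37; negative if 3 or fewer succeed. Not-promising rate 5%, promising rate 20%, both error limits 0.10.

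**Step 1: reproduce the stated design.** With X1 ~ Bin(12, p) and X2 ~ Bin(25, p),

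P(positive) = sum over x = 1 to 12 of P(X1 = x) × P(X2 ≥ 4 − x).

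At p = 0.05:

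- x = 1: 0.3413 × 0.1271 = 0.0434
- x = 2: 0.0988 × 0.3576 = 0.0353
- x = 3: 0.0173 × 0.7226 = 0.0125
- x ≥ 4: 0.0022

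The total is 0.0935 before rounding of the terms. At p = 0.20 the same sum gives 0.9024. Both agree with the stated 0.90 figures. The chance of opening stage 2 at 5% is 1 − 0.95^12 = 0.460.

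**Step 2: how large could the affected group be?** Let q be the proportion of patients who die of a clearly unrelated cause before progression and within six months. The documents give no value, so every q below is an assumption. Most patients progress first, which keeps q small. With constant hazards, any-cause six-month PFS of 5% and six-month non-disease mortality m,

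q = 0.95 × [−ln(1 − m)] / [−ln(0.05)].

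For m = 1%: 0.95 × 0.01005 / 2.9957 = 0.0032. For m = 2% and 3%, q = 0.0064 and 0.0097. Flat values of 1% and 2% are added as a wider range.

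**Step 3: natural reading.** A patient who has died is not progression free at six months, so the patient is not a success under either rule. P(positive) at 5% stays 0.0935.

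**Step 4: only the first-stage phrase is read the other way.** Stage 2 opens if any of the 12 is a true success or such a death; the final count uses true successes only.

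- P(open) = 1 − (0.95 − q)^12
- P(positive) = 0.0935 + [0.95^12 − (0.95 − q)^12] × P(X2 ≥ 4), where P(X2 ≥ 4) = 0.0341 at 5%

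| q | P(open stage 2) | P(positive) |
|---|---|---|
| 0 | 0.460 | 0.0935 |
| 0.32% | 0.481 | 0.0942 |
| 0.97% | 0.522 | 0.0956 |
| 1% | 0.524 | 0.0957 |
| 2% | 0.581 | 0.0976 |

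If exactly one such patient falls among the first 12, stage 2 is certain to open, and that patient is the only reason with probability 0.95^11 = 0.569. Under the constant-hazard values, the chance of at least one such patient among 12 is 1 − (1 − q)^12, which is 0.04 to 0.11.

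**Step 5: counted as a success in both rules, with 5% as the true any-cause rate.** Replace p by 0.05 + q in the Step 1 formula. For m = 1%, 2% and 3%, P(positive) is 0.110, 0.129 and 0.149. This is the only reading here that exceeds 0.10.

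**The case against.** The strongest reply is that not being an event is different from being a success. The hypotheses are PFS rates. The first-stage rule is restated in PFS terms in the same paragraph, and the final rule counts patients who are progression free. Only the isolated first-stage phrase allows the adverse reading. A reader might infer that a drug-related death would count as a success and that type I error is therefore inflated. The documents do not say so, and Step 5 needs both rules read against their natural sense. If 5% and 20% were meant as disease-only rates, there is no inflation even then. This part of the reply stands.

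A reader might also infer a conflict with the other time-to-event endpoints, since time to treatment failure includes "death due to any cause, or early discontinuation of treatment" and time to death also counts every cause. Those are different endpoints. Survival counts all deaths by nature, and treatment failure is a deliberately broader composite. They show that any-cause wording was available, not that the primary rule contradicts them.

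Nor would such a death be hidden: cause of death is recorded (Section 13), fatal events are reportable as serious (Section 17.2), and survival is followed (Section 4.1). That is correct, but it does not settle the primary count. The mismatch between the endpoint's name and its stated event rule remains, as do the three wordings of success.

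**Conclusion.** The concern holds as an inconsistency between the endpoint's name and its event rule, with an unstated consequence for the decision counts. Confidence in the textual mismatch is high. The numerical consequence depends on the reading:

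- **Natural reading:** no change in error rates.
- **First-stage wording only:** type I error 0.094 to 0.098 for an assumed 0.3% to 2% of patients, still within 0.10. The chance of opening stage 2 at 5% rises from 0.460 to between 0.481 and 0.581.
- **Success in both rules:** type I error 0.110 to 0.149, for an assumed 1% to 3% six-month non-disease mortality under constant hazards.

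Such deaths are probably few, because uncertain deaths already count as progression and most patients progress first. The finding does not show an error in the sample size, the cut-offs or the stated error rates. It should be fixed because the rule as written does not give the quantity named, and because the correction costs little.

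**What to change.** In Section 12 and the Biostatistics section, define the primary event as progression or death from any cause. Define success as alive and progression free at six months, and use that one phrase in the first-stage rule, its restatement and the final rule. Drop the progression-rate label for the endpoint. The exemption for clearly unrelated deaths may stay in the objective-status definitions.

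**Cost.** Wording only. The 12 and 37 patients and both cut-offs stay, and no extra data are needed. The observed six-month PFS may be slightly lower. If 20% was meant as a disease-only rate and a fraction f of successes become failures, power is that of Step 1 at 0.20 × (1 − f): 0.899, 0.890 and 0.882 for f = 1%, 3% and 5%, against 0.902, so slightly under the stated 0.90. If 5% was also disease-only, type I error falls from 0.0935 to 0.091, 0.086 and 0.081.

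**Separate, secondary clarifications** that could go into the same amendment: one start date (Section 12 names registration but then calculates from first dose, or first post-operative dose on the surgical arm); how a patient with Unknown status at six months is counted; and an assessment window that fits eight-weekly scans. None of these follows from the event rule.

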## **OBJECTIVES AND SCIENTIFIC AIMS**

- Primary aim:
  - Determine the efficacy of perifosine in patients with recurrent/progressive GBMs not taking EIAEDs as measured by 6mPFS.
- Secondary aims
  - Determine molecular effects of perifosine on AKT, RAS, and proliferation in malignant gliomas by analysis of resected tissue in patients on the surgical substudy.
  - Determine metabolic effects of perifosine on malignant gliomas by PET imaging.
  - o Identify molecular features that predict perifosine response.

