## IRB#: 06-044 A(11)

the drug is considered promising (defined above) after either the first stage enrolling 12 patients with GBM or complete accrual of the total cohort of 37 patients with GBM. Any additional patients enrolled through this mechanism will be included in the primary analysis of efficacy (6mPFS) and the total cohort will be increased from 37 patients with GBM to a maximum of 47 patients with GBM (37 + 10 additional surgical patients in the unlikely circumstance that none of the initial 37 patients are enrolled on the surgical arm). Therefore, the maximum enrollment is up to 57 patients (37 with GBM, not on surgical substudy; up to 10 additional patients with anaplastic glioma; up to 10 additional patients on surgical stubstudy if not already accrued).

Although patients on the surgical substudy will have resections of tumor at the initiation of treatment, the natural history of recurrent GBM strongly supports the concept that nearly all patients will have tumor progression by 6 months if no further treatment or ineffective treatment is provided post-operatively. For example, a review of patients with recurrent GBM treated for first relapse at the MD Anderson Cancer Center also supports the concept that gross total resection does not impact on 6-month PFS rate. During the time from of 2001-2003, 220 patients were treated at MD Anderson for first relapse or progression of GBM. There was no difference in 6-month PFS between those patients who had a gross total resection at relapse compared with all other patients. Hence, we plan to combine data from patients on and not on the surgical substudy in efficacy analyses.

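### The 5% null rate has no stated basis and is one third of the 15% historical value named for comparison, so a positive result should be limited in advance to a rate above 5%

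*Combined protocol and SAP*

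**What the plan says.** The primary aim in Section 2.0 is: "Determine the efficacy of perifosine in patients with recurrent/progressive GBMs not taking EIAEDs as measured by 6mPFS".

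Section 14.0 (Biostatistics) begins with the comparator: "The historical values for comparison are from a database of 225 GBM patients enrolled in 8 previous phase II studies". It describes those treatments as not particularly effective and gives their result: "In this database, the 6 month PFS was 15% for GBM". It adds 17.5% on BCNU, a figure that also appears in Section 3.1. From these it infers: "Therefore, we would expect 6 month PFS to be less than 20" (per cent).

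The design follows directly. A 20% rate is promising and "a 6 month progression free survival rate of 5% is considered not promising", with both error probabilities set at 0.10. Accrual stops if 0 of the first 12 GBM patients are progression-free at 6 months. Otherwise 25 more are enrolled, and "if 3 or less patients with GBM are progression free at 6 months, the study will be declared negative". The section closes with the operating characteristics at 20% and 5%.

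Two further statements bear on the point. Section 14.0 keeps anaplastic glioma out of the efficacy analysis because "the historical controls for patients with anaplastic glioma are less well defined than for GBM". The surgical-arm subsection, in arguing for pooling surgical and non-surgical patients, says that "nearly all patients will have tumor progression by 6 months if no further treatment or ineffective treatment is provided post-operatively".

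**The concern.** The null rate defines a false positive. Here it is 5%, while the only 6-month PFS rates the plan cites for recurrent GBM are 15% and 17.5%. No section of the available text derives 5% or links it to those figures. The historical data support a statement about the upper design rate (below 20%) and then drop out of the argument.

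The plan does treat historical control as important: poorly defined controls are its reason for leaving anaplastic glioma out of the efficacy analysis. A reader told that the trial was positive for efficacy would naturally set the result against 15%. The section says when the trial is negative. It does not say what a positive result permits one to conclude about the values it introduced for comparison.

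**Working it through.** **Inputs, all from Section 14.0.** First stage 12, stop at 0; total 37 (12 + 25), positive at 4 or more; null 5%, alternative 20%, errors 0.10 and 0.10; historical values 15% (225 patients, 8 studies) and 17.5%.

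**1. Reproduce the plan's figures.** With X the first-stage count,

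P(positive | p) = Σ over x = 1 to 12 of P(Bin(12, p) = x) × P(Bin(25, p) ≥ 4 − x).

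- At 5%: x = 1 gives 0.3413 × 0.1271 = 0.0434; x = 2 gives 0.0988 × 0.3576 = 0.0353; x = 3 gives 0.0173 × 0.7226 = 0.0125; x ≥ 4 gives 0.0022. The sum is 0.093, so P(negative) is 0.907.
- At 20%: 0.1859 + 0.2757 + 0.2353 + 0.2054 = 0.902.

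Both meet the stated 0.10 and 0.90. A search over two-stage rules returns 0/12, 3/37 as the Simon optimal design for 5% against 20%. The arithmetic is sound.

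**2. Apply the same rule at other true rates.**

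| True 6-month PFS | P(stop at 12) = (1 − p)^12 | P(positive), n = 37 |
|---|---|---|
| 5% | 0.540 | 0.093 |
| 8% (assumed) | 0.368 | 0.294 |
| 10% (assumed) | 0.282 | 0.447 |
| 15% | 0.142 | 0.751 |
| 17.5% | 0.099 | 0.843 |
| 20% | 0.069 | 0.902 |

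The 8% and 10% rows cover the possibility that this trial's patients would do worse than the historical ones.

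**3. Place the smallest positive results.** 5%/15% = 1/3. 4/37 = 10.8% and 5/37 = 13.5%, both below 15%; 6/37 = 16.2% is the first count above it. At a true 15%, the chance of a positive result from exactly 4 or 5 is 0.751 − 0.464 = 0.287, where 0.464 is the probability of continuing and reaching 6 or more.

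**4. Allow for uncertainty in the 15%.** The plan gives no count. Assuming 34/225 = 15.1%, a simple binomial and no variation between the 8 studies, the exact 95% interval is 10.7% to 20.5%. P(positive) runs from 0.50 to 0.91 over that range. Both 10.8% and 13.5% lie inside it, the first only just; 5% lies well outside.

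**5. Ask what the final count can exclude.** For a two-stage adjusted interval, rank an early stop below any continuation and then order by total count. The lower limit solves P(S ≥ x | p) = 0.10 and the upper limit P(S ≤ x | p) = 0.10. This gives an 80% two-sided interval, matching the one-sided 0.10.

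| Final count | Rate | Adjusted 80% interval |
|---|---|---|
| 4/37 | 10.8% | 5.1% to 22.0% |
| 5/37 | 13.5% | 6.9% to 24.6% |
| 7/37 | 18.9% | 10.9% to 30.1% |

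The minimum positive result excludes 5%, narrowly, and contains 15%, 17.5% and 20%. At two-sided 90% and 95%, its lower limits are 4.0% and 3.2%. The first count whose 80% lower limit passes 15% is 9/37 (15.3%). If 9 of 37 were the criterion, error at a true 15% would be 0.091 and power at 20% only 0.311.

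**6. Check the surgical extension.** The surgical-arm subsection adds any extra surgical patients to the primary analysis, up to 47 GBM patients. With 12 + 35 patients and the cut-off assumed to stay at 4, P(positive) is 0.156 at 5% and 0.824 at 15%.

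**The case against.** The strongest reply is that nothing here is an error. The plan ties its error rates openly to 5% and 20%, defines a type I error as accepting a non-promising therapy, and never claims superiority to 15%. In a single-arm screening design the uninteresting rate need not equal a historical mean. All of that stands. A reader might infer that the real type I error is 0.75 or that the plan promises to beat 15%; the documents support neither reading.

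A reader might also infer that the historical controls play no part in the decision rule. That goes too far: the text moves from 15% and 17.5% to an expectation below 20% and then adopts 20% as promising, so the controls appear to inform the upper rate. Only the lower rate is unexplained.

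Third, these patients may have a lower background rate than 15%: Section 6 admits KPS of 50 or above and any number of prior relapses. That is possible, and step 2 shows its effect (0.29 to 0.45 at 8% to 10%). But the plan does not make the argument, and neither criterion yields 5%. The remark that nearly all patients progress gives no rate and is there to justify pooling.

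Last, calling 4 or 5 of 37 below the comparator sets one point estimate against another. This is fair: both lie within the historical figure's sampling uncertainty, which is probably wider than step 4 shows because variation between studies is ignored. Such a result would not show perifosine to be worse than the historical treatments.

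**Conclusion.** The concern holds as a gap in justification and interpretation. The rule is correct for 5% against 20%, but 5% is unsupported. With 37 patients, a drug performing at the plan's own 15% would be called positive about three times in four (0.75), and at 17.5% with probability 0.84. Meeting the criterion is therefore evidence of a rate above 5% and not, by itself, evidence of efficacy beyond the cited treatments.

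Two stronger conclusions are tempting and should be resisted. One is that every positive result supports only a rate above 5%. The limit attaches to meeting the criterion: treating 15% as fixed, 9/37 would have an adjusted lower limit of 15.3%. The other is that the trial should be redesigned to test 15%. The 37 patients cannot separate 20% from 15% (power 0.31), and the documents do not say that this was the aim.

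The probabilities assume exact binomial counts, complete 6-month status and n = 37. The historical interval rests on the assumed 34/225. The gap should be closed before the result is read, but it does not undermine the design.

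**What to change.** Keep the design, the sample size, the 4-of-37 cut-off and both historical figures; removing the 15% and 17.5% would make the plan less transparent. Add to Section 14.0:

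> Meeting the 4-of-37 criterion shows only that 6-month PFS exceeds 5% at one-sided 0.10; it does not by itself show efficacy beyond the cited historical rates (probability of a positive result with 37 patients: 0.75 at a true 15%, 0.84 at 17.5%). The final rate will be reported with a two-stage adjusted confidence interval, with level and ordering stated in advance, beside 15% and 17.5%, and any statement relative to those rates will rest on that interval.

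An 80% two-sided interval matches the plan's one-sided 0.10, but the choice of level is the authors'. If there is a source for 5% in this population, cite it.

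The inserted probabilities hold for n = 37 only. If the surgical extension is used, they must be recomputed for the actual total and the cut-off for that total stated. With the cut-off left at 4 and 47 patients, the chance of a positive result at 5% is 0.16, so the claim of exceeding 5% at one-sided 0.10 would no longer hold.

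The cost is two sentences, one interval and, if available, one citation, with no extra patients. The downside is a weaker permitted conclusion from a minimally positive result; even 7/37 has an interval that contains 15% and 17.5%.
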